This study is designed to assess the efficacy of a pre-existing school-based physical activity program, BOKS (“Build Our Kids Success”). BOKS is a before-school physical activity program that is currently present in over 2500 schools nationwide and internationally. Through this program, children in grades K-8 participate in before school physical activity sessions. Trained volunteers lead each session using a core curriculum developed by the BOKS leadership team that includes a warm-up game followed by activities such as relay races or obstacle courses, with a focus on a new “skill of the week” each week. In prior research, BOKS has been shown to improve child BMI as well as measures of social-emotional wellness over the 12-week program.¹²

Prior studies of physical activity interventions raise questions on whether the programs are sustainable and feasible following the end of the study period. The use of a pre-existing physical activity program aims to overcome these concerns. Additionally, by examining our primary and secondary outcomes in the BOKS program, we are evaluating the effect of the program as implemented in a real-world setting. Given the large reach of this program, the findings from this study are potentially generalizable to a larger population of students who are participants nation-wide.

III. Study Populations and Recruitment

Setting and Study Population

Students will be recruited within each of the three schools for participation in the BOKS before-school physical intervention. The participating schools include 1 middle school (541 enrolled students) and 2 elementary schools (494 and 370 enrolled students each). A flyer will be sent home with all children for program participation and parental consent/child assent for research trial participation. Target recruitment is 120-150 students total in the Spring 2018 session (40-50 per school) and 120-150 students in the Fall 2018 session (40-50 per school), for total N=240-300. Students are eligible for participation if they are in grades K – 8 with enrollment in BOKS program. The inclusion of a wait-list control group is to ensure equipoise, and that all interested students have the opportunity to participate in the physical activity program.

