Students are eligible for participation in BOKS if they are (a) enrolled in the school in grades K-8 with (b) signed BOKS parental release form. In the school that independently held BOKS in Fall 2017, preference will be given to students who have not yet participated. Beachmont Elementary will limit participation to 1st through 5th grades as kindergarten students follow a different schedule.

Spring 2018 Session

For Beachmont Elementary and Garfield Middle School:

All students will receive the BOKS Registration packet approximately 3-4 weeks before their schools' planned start date that will include the following below. Recruitment information will explain that we are interested in better understanding the effects of physical activity programming on child physical health, quality of life, and school performance.

BOKS in Revere Detailed Protocol

Study PI: [name], MPH

- (1) Letter introducing the BOKS program and the research study
- (2) Fact sheet answering key questions regarding the program and study
- (3) BOKS Registration form

Children will be instructed to return the BOKS Registration Form if they would like to participate in the BOKS program. Once the BOKS Registration Form is received, children will then receive Research Consent Form in school to take home for their parents to review, to be completed if they would additionally like to participate in the BOKS study. All forms should be submitted approximately 1-2 weeks before the start of the Spring 2018 program.

In order to ensure equal access to the program, participation in the BOKS program will be by lottery and not first-come, first serve. This decision was made in conjunction with school principals to not give preference to students who turned in forms first. All children with completed BOKS registration forms-will be entered in the lottery. The lottery is held in partnership with schools and independent of the research process, and will be held following return of BOKS registration forms. Children may participate in BOKS without participating in the research study. If registration does not exceed 50 students for the Spring 2018 session, there will be no waitlist control group or need for randomization.

See schema for detailed timeline.

For Paul Revere Innovation School:

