As described above, this school has a pre-existing BOKS program that is independent of the research intervention and occurs as part of school-wide before school enrichment programs. Per school preference, enrollment target is approximately 40-50 students. Within this school, enrollment in the BOKS program occurs through standard school procedures for before school enrichment enrollment. Once the school has confirmed their enrollment for the Winter/Spring 2018 session, enrolled students will receive documents specific to Paul Revere, including:

- 1) BOKS study Introduction letter and Fact Sheet (Appendix 12a)
- 2) Research Consent Form (Appendix 12b)

As there will be no control group and no lottery for enrollment within this school, these documents are modified from those distributed to the other two schools and will only cover the research evaluation (not randomization and enrollment process).

Fall 2018 Session

Modifications will be made to Fall 2018 enrollment procedures based on discussions with schools as well as experience with Spring 2018 session. As program enrollment did not reach capacity in Spring 2018, no

BOKS in Revere Detailed Protocol

Study PI: [name], MPH

lottery was held and all interested students were able to participate in the program. As a result, there was no wait list control group.

In discussion with participating schools, first-come, first-serve registration will be used for Fall 2018 for consistency and no lottery will be held. If the BOKS program does not reach capacity, program registration will be accepted until program is full (40-50 students). To ensure equal access, preference will be given to students who have not previously participated in the BOKS program. In discussion with school principals, a poster (Appendix 14) will be added to increase recruitment.

In order to ease the burden of paperwork distributed via the schools, paperwork will be distributed in the following order:

1. Follow-up Letter to Previous Participants (Distributed in schools **only to consented study participants**, in envelope with student's name on it) – Appendix 15
2. Introductory letter and Fact Sheet, with Interest Form for students to return if interested (Distributed to **ALL** students) – Appendix 16
3. BOKS registration (Distributed **only to students who return Interest Form**, to be returned prior to program start) – Appendix 6b

Consent

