Randomization will not be included in Fall 2018 enrollment procedures. Enrollment in the BOKS program will be first-come, first-come at each school with goal enrollment of 40-50 students at each school (120-150 students total), with preference given to students who have not yet participated in the BOKS program. This decision was made with input from school principals and BOKS session leaders.

IV. Study Visits and Data Collection

This study is a collaborative effort of key stakeholders, including Revere community health infrastructure (RevereCARES), the Revere School District, the BOKS program, and this research team. Initial conversations with stakeholders began in Summer 2017, following which an internal implementation grant was awarded in October 2017 from the MGH Executive Committee on Community Health, with the aim of improving health equity. Additional conversations have continued with stakeholders regarding planned study procedures, pending IRB approval.

Phase I

In the initial qualitative phase of the study, we will perform semi-structured qualitative interviews with parents to assess barriers to physical activity and the role that school based interventions may play in reducing barriers. Parents will be recruited from those students participating in an independently initiated Fall 2017 BOKS program occurring in one of the participating schools. If recruitment goal is not met, parents will be recruited from the Spring 2018 BOKS session.

BOKS in Revere Detailed Protocol

Study PI: [name], MPH

A handout will be sent home with students participating in BOKS with a fact sheet explaining the study and a form to return if parents would like to be contacted for a telephone interview. After obtaining verbal consent via telephone, parent will be asked a series of questions related to their perceptions of the BOKS program as well as barriers to physical activity (See Appendix 1). The interview will be led by trained research staff and will take about 20-30 minutes.

In addition, we will perform an observation of a BOKS session using SOFIT, a structured observational tool for physical activity.

Phase II

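### The Phase II total of 240-300 counts every programme place in two full sessions and was not revised after Spring 2018: as distinct consented children, 300 is out of reach at 50 places per school and 240 is doubtful

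*Combined protocol and SAP*

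**What the plan says.** Section III, Setting and Study Population, gives a Spring 2018 target of 120-150 students (40-50 per school) and the same target for Fall 2018, "for total N=240-300". Eligibility is tied to the programme: "Students are eligible for participation if they are in grades K – 8 with enrollment in BOKS program".

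Other parts of the same 8/9/2018 version bear on that total:

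- **Capacity.** Section III, Fall 2018 Session, describes a full programme as 40-50 students. Randomization, Fall 2018, repeats 40-50 per school (120-150 in all) as goal enrolment.
- **Spring result.** The Fall 2018 Session text states "As program enrollment did not reach capacity in Spring 2018", and goes on to say that there was no lottery and no wait-list control group. No Spring count is given.
- **Consent.** Section III, Spring 2018 Session: "Children may participate in BOKS without participating in the research study". No expected consent rate is given.
- **Returners.** Consent, Fall 2018, offers Spring participants the programme again. It also says their Spring consent covers Fall measurement whether or not they attend in Fall. Randomization, Fall 2018, fills places "with preference given to students who have not yet participated in the BOKS program", which limits returners without excluding them.
- **A different Spring goal.** Randomization, Spring 2018, aims for 80-100 students per school, half intervention and half wait-list control. The school with a pre-existing programme is not randomized.
- **Age limit.** Section V takes the cognition and quality-of-life measures only in children aged 8 or over.

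**The concern.** This is the only overall sample size stated for Phase II, and a reader will take it as the number of children to be analysed. Section VI supports that reading, because it makes the child the unit of analysis. Yet the figure is a count of programme places, set before Spring 2018 was run and left unchanged when the Spring result was written into the protocol.

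Two things are at stake. First, the stated size no longer describes the design that remains: Spring is complete, it fell below capacity, and it supplied no wait-list controls. Second, the plan does not say whether N counts children or child-sessions. Spring children measured again in Fall could enter twice, and the planned t-tests and regressions have no provision for repeat participation.

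**Working it through.** **Reproducing the stated figure.** Inputs: 3 schools, 40-50 places per school, 2 sessions (section III).

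- Low end: 3 x 40 x 2 = 240.
- High end: 3 x 50 x 2 = 300.

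Both ends match. The protocol gives no alpha, power, effect size, SD or dropout rate, so no sample-size formula lies behind the total.

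**Distinct consented children.** Let c be places per school, f the share of Spring places filled, r the share of Fall places taken by Spring returners, and q the share of enrolled children with research consent. With Fall full:

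N = (3c x f + 3c x (1 - r)) x q

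The stated total is the case f = 1, r = 0, q = 1. The protocol itself says f is below 1. Values for f, r and q below are assumptions.

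**Ceiling.** Take the mildest shortfall, one child at each school in Spring, with Fall full, no returners and full consent:

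- c = 50: 3 x 49 + 3 x 50 = 297, below 300.
- c = 40: 3 x 39 + 3 x 40 = 237, below 240.

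If only the two lottery schools were each one short, the figures are 298 and 238. The Spring shortfall alone therefore need not remove many children; consent and returners could remove many more.

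**Consent needed to reach 240 with 50 places per school.** Required q = 240 / (150f + 150(1 - r)).

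| Spring fill (assumed) | No returners | 10% returners |
|---|---|---|
| 90% | 240/285 = 84% | 240/270 = 89% |
| 80% | 240/270 = 89% | 240/255 = 94% |
| 70% | 240/255 = 94% | 240/240 = 100% |
| 60% | 240/240 = 100% | 240/225, above 100% |

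At 45 places, 90% fill and no returners, the requirement is 240/(121.5 + 135) = 94%. At 40 places, 240 cannot be reached at any consent rate.

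**Illustrations only.**

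- c = 50, f = 0.9, r = 0.1, q = 0.9: (135 + 135) x 0.9 = 243.
- c = 50, f = 0.8, r = 0.2, q = 0.8: (120 + 120) x 0.8 = 192.
- c = 40, f = 0.9, r = 0.1, q = 0.9: (108 + 108) x 0.9 = 194.

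**The two Spring targets.** Setting and Study Population gives 3 x 40-50 = 120-150 for Spring. Randomization, Spring 2018, gives 80-100 per school, or 3 x 80-100 = 240-300 in Spring alone if applied to all three schools. One school has no control group, so a consistent Spring figure would be 2 x 80-100 + 40-50 = 200-250. These passages do not agree. Adding 40-50 new Fall children at the non-randomized school brings 200-250 back to 240-300, which may be how the total was meant, but the protocol never sets that sum out.

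**The case against.** The best defence is that falling short of capacity is not the same as falling short of target. With a capacity of 50, a school enrolling 40-49 children is below capacity yet inside the 40-50 target, and the absence of a lottery fits that. This stands. A reader might infer that the whole range 240-300 is undeliverable, but the documents do not support it: no Spring count is given, and one of the illustrations above reaches 243.

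Second, 50 may not be a hard cap. Section IV and the text on the pre-existing programme say approximately 40-50, and Fall enrolment is called a goal. This stands as a condition on the statement about 300.

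Third, N might mean child-sessions. Spring children measured again in Fall would then count twice, even without a Fall place, and 240-300 could be reachable. The text does not exclude this. It would, however, sit badly with the child as unit of analysis, and it shows that the unit needs defining.

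Fourth, the preference for newcomers limits returners, and the schools enrol 541 + 494 + 370 = 1,405 students, so new children need not be scarce. This is fair, and it is why the zero-returner column is shown.

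A reader might also infer that precision or power is overstated. The protocol states neither, so there is nothing to overstate. Nor does it claim 240-300 for the measures restricted to age 8 or over; that restriction is openly stated.

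**Conclusion.** The point holds in a limited form. The total equals every programme place in two full sessions and was not updated in the version that reports the Spring shortfall. As distinct consented children, 300 is unattainable if 50 places per school is the limit. The lower end of 240 is doubtful but open: it needs 84-89% consent at 80-90% Spring fill with 50 places, a full Fall and no returners, and more than that with returners or fewer places.

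The conclusion about 300 rests on the protocol's own statements plus the two readings named, a cap of 50 and distinct children. The consent thresholds rest on assumed fill and returner rates. No single expected N can be derived, and any such figure would be illustrative. The number aged 8 or over cannot exceed the overall N and should be smaller wherever younger children enrol, but its size cannot be derived either. The absence of Spring wait-list controls does not by itself reduce the number of places; it changes who makes up the sample. The problem is a stale and undefined sample size, correctable from counts the study team should already hold.

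**What to change.** In section III, Setting and Study Population:

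1. Replace the 240-300 total with the actual Spring 2018 number of distinct consented, measured children plus the Fall 2018 ceiling for newly consented children.
2. State that N counts distinct children, and report Spring children re-measured in Fall on a separate line.
3. State beside the total that Spring contributed no wait-list controls.
4. Give separately the expected number aged 8 or over, for the Flanker test and PedsQL.
5. Reconcile the Spring target of 40-50 per school with the 80-100 per school in Randomization, Spring 2018, noting that one school was never to have controls.

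The cost is protocol wording and a tabulation of Spring records. The stated number will probably be less favourable. No additional enrolment, measurement or procedure is requested.

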For schools without a pre-existing BOKS program, parents will complete and return the Program Registration Form if they are interested in enrolling their child in the BOKS program. For schools with a pre-existing BOKS program in which students are already registered, study consent will include sharing of registration form with the research team. For all schools, parents who enroll their children in BOKS will complete the Research Consent Form (sent home after program registration) if they accept participation in the BOKS study. Children can participate in BOKS without participating in the research study. Parents will return the Consent Form directly to the research team in an addressed and stamped envelope to be mailed. Given that schools work within a fixed timeline with limited flexibility of changing program schedule and potential delay in delivery of consent forms via mail, students may also turn research consent forms in sealed envelopes to school to be picked up by research staff and transported to MGH. In further discussion with principals, they recommended this additional option as well for consent form return to minimize burden on parents in the event they cannot make it to the post office/mail box. Families may also receive a second consent form if requested.

Completed consent form to be stored in a locked file as well as documented in REDCap, including date of consent. The PI/Project Manager will review consent forms for accuracy and completeness, in addition to monitoring study process and outcomes regularly.

Given the different study recruitment between schools based on school needs, different consent form and accompanying letters will be distributed to students based on school (Appendix 6 for schools without pre-existing programs; Appendix 12 for schools with pre-existing programs).

Fall 2018

For students who consented for research study participation in the Spring 2018 BOKS session, research consent included Fall 2018 study participation (collection of baseline and follow-up measures) regardless of Fall 2018 BOKS program participation. While these participants will not be re-consented this Fall, these children will again be offered the opportunity to participate in the BOKS program and program materials sent home will give the option of declining study

BOKS in Revere Detailed Protocol

Study PI: [name], MPH

participation if desired. A letter will be sent home to consented participants explaining these options (Appendix 15).

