primary analyses will be based on change from baseline to follow-up with each outcome variable, with comparison performed between intervention and control group at each time. For all continuous variables, we will use t-tests for initial comparison between groups, followed by linear regression to control for potentially confounding variables (age, sex, school, SES) or potential effect modification (program attendance/MVPA level, parental PA support, baseline PA level, baseline BMI). For all binary variables, we will use Chi Square tests to evaluate for differences between groups at baseline and follow-up, followed by logistic regression to evaluate for confounding or effect modification. All analyses will be done in SAS under the guidance of a statistician.

Transcriptions from qualitative interviews will be reviewed by two study staff members to identify themes. Results from structured physical activity observation will provide descriptive statistics regarding individual program content and will be used as a measure of program implementation along with accelerometer data.

VII. Monitoring and Quality Assurance

Data security & privacy:

Paper data collection forms will be stored in a locked and secure facility only accessible by research staff at MGH in the Division of General Pediatrics at [name]. All data collected and recorded on paper forms will be entered into a Partners supported REDCap database. Only approved study staff will have access to identifiable information and the linking code. Research staff will track all communication made with parents this database including parent was contacted about the study, if the child was eligible and interested in participating, and demographic information (age, gender, parent contact info). This database will be housed on the Partners network and accessible to only IRB approved study staff.

The NIH Toolbox data will be stored on password protected iPads. The NIH Toolbox iPad application is encrypted and sends data exports (in .csv format) and participant reports (in .txt format) via secure email.

All collected data will be identified with a subject ID number only so that it cannot be matched with an individual child.

For the qualitative portion of the study, telephone interviews with parents will be recorded. To protect confidentiality, these recordings will be stored in a Partners SFL, a HIPAA compliant and encrypted format.

Maintaining the integrity of the technology

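### Section VI has no session term, no prior-BOKS term and no allowance for children measured twice, although prior BOKS is not an exclusion and Spring children are measured again in Fall

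*Combined protocol and SAP*

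**What the plan says.** **Admission.** In Section III (Recruitment, Phase II), eligibility needs enrolment in grades K-8 and a signed release; earlier BOKS is not an exclusion. For the school that ran its own BOKS programme in Fall 2017, the text adds that "preference will be given to students who have not yet participated". For Fall 2018, Section III (Fall 2018 Session) says that "preference will be given to students who have not previously participated in the BOKS program", and the Randomization section repeats this: "with preference given to students who have not yet participated in the BOKS program". Fall registration stays open until the programme is full. On Spring, the same section reports: "As program enrollment did not reach capacity in Spring 2018". No lottery was held and no wait-list control group was formed.

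**Repeat measurement.** Section III (Consent, Fall 2018) says of consented Spring participants that "research consent included Fall 2018 study participation (collection of baseline and follow-up measures) regardless of Fall 2018 BOKS program participation", and that "these children will again be offered the opportunity to participate in the BOKS program". Section IV schedules measures in both sessions regardless of group.

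**Analysis.** Section III (Setting and Study Population) adds the two session targets into a total of 240-300. Section VI takes the child as the unit of analysis and describes one change-from-baseline comparison: t-tests, then linear regression. The adjustment list is given as "potentially confounding variables (age, sex, school, SES" and ends there. The effect modifiers are attendance/MVPA, parental support for activity, baseline activity and baseline BMI. Session and prior BOKS appear in neither list, and there is no rule for a child with records in both sessions.

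**The concern.** A preference rule keeps repeaters out only when places run short. Spring fell short of capacity, Fall stays open until full, and Spring families are invited back, so repeat participation is a foreseeable part of the data. For a repeater, the Fall baseline comes after a complete course. Section II itself says that BOKS has improved BMI and social-emotional wellness over 12 weeks, so by the protocol's own premise that baseline is not a pre-programme value.

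Two things are at stake. The first is what the estimate means: if it averages first and repeat courses over two seasons, it is neither a first-course effect nor a repeat-course effect. The second is precision: t-tests and ordinary regression treat two records from one child as independent.

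The listed covariates do not repair this. Under Section IV a parent who completed the survey in Spring does not receive it again in Fall. A repeater's parent-reported activity and support values may therefore date from the Spring session, and they do not record prior exposure.

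**Working it through.** **1. The plan's own figure.** 3 schools × 40-50 = 120-150 per session; × 2 sessions = 240-300. This reproduces the stated total, but as a count of programme places. If a share q of Fall places goes to Spring children (q is assumed; the documents give no count), the number of distinct children is (120 to 150) × (2 − q):

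| q | Distinct children |
|---|---|
| 0 | 240-300 |
| 0.10 | 228-285 |
| 0.20 | 216-270 |
| 0.30 | 204-255 |

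**2. Mixing first and repeat courses.** Let p be the share of repeaters among intervention records and r the repeat-course gain as a fraction of the first-course gain. With comparators who do not change, the estimate as a fraction of the first-course effect is 1 − p(1 − r). Both p and r are assumptions.

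| p | r = 0 | r = 0.5 | r = 1 | r = 1.25 |
|---|---|---|---|---|
| 0.20 | 0.80 | 0.90 | 1.00 | 1.05 |
| 0.30 | 0.70 | 0.85 | 1.00 | 1.075 |

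Shrinkage is 10-20% at p = 0.20 and 15-30% at p = 0.30 for r between 0.5 and 0. It is nil at r = 1, and above that the estimate is inflated.

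**3. Effect on power (illustration).** The protocol states no alpha, power or effect size. Assume two-sided 5% and 80% power for the undiluted effect. With f the fraction from step 2, power is about Φ(2.80f − 1.96): 71% at f = 0.90, 66% at 0.85, 61% at 0.80 and 50% at 0.70.

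**4. Already-exposed comparators.** Spring had no control group and Fall is not randomized. The only Fall non-participants the text clearly provides for are consented Spring children, who have already had a course. If they make up all the comparators and change by k times the first-course gain, the fraction is 1 − p(1 − r) − k. At p = 0.20 and r = 0.5 this is 0.90 − k:

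- k = 0.3 (they go on gaining): 0.60
- k = 0 (no change): 0.90
- k = −0.5 (they lose ground after stopping): 1.40

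The bias can go either way.

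**5. Repeated children.** With n records, m children contributing two each, and within-child correlation ρ between the two change scores, the variance of a mean is (σ²/n)(1 + 2mρ/n); the planned methods use σ²/n. If ρ is positive, the standard error is too small when both records fall in the same group, and can be too large when one is a Spring participant record and the other a Fall comparator record. The documents give neither m nor ρ, so no size can be attached.

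**The case against.** **Pooling is not stated.** This is correct. Section VI never says in words that the sessions are combined, and it refers to comparing groups at each time. Pooling is inferred from one analysis description and one summed target. Silence on the matter is itself the gap.

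**Dilution toward zero.** A reader might infer that repeaters necessarily pull the estimate toward zero. That requires a repeat course to add less than a first one, which the documents do not say. Steps 2 and 4 show that inflation is also possible.

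**Spring turned no repeater away.** A reader might also infer this from the unfilled capacity. The capacity statement explains why no lottery was held. The school with Fall 2017 BOKS never had a lottery and enrolled through its own procedures, so the statement does not clearly cover it. Documented exposure before Spring is confined to that school, about one third of planned places (40-50 of 120-150), and school is already a covariate. This limits the Spring part of the problem but not the Fall part.

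**Prior exposure is already on file.** This holds for session and for Spring 2018 attendance. No section says that Fall 2017 participation is captured as study data.

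**Real-world effect.** The protocol aims to evaluate the programme as implemented, and children may re-enrol. A mixed estimate is a legitimate target if it is declared, but Section VI does not declare it and would still need to handle correlated records.

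**Conclusion.** The point stands as an omission. Prior BOKS is not an exclusion, Spring children are measured again in Fall, and Section VI has no session term, prior-BOKS term or within-child correlation. If the sessions are combined, the estimate mixes first and repeat exposure and season, may be biased in a direction the documents do not settle, and carries standard errors that ignore repeated children.

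The 10-30% shrinkage rests on assumed inputs (20-30% repeaters, repeat gain 0 to 0.5 of the first) and on comparators who do not change. It illustrates scale and does not estimate the bias in this study. The true repeater count may be small if new children fill the Fall places.

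**What to change.** In Section VI:

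- add session (Spring/Fall) and prior BOKS participation (Fall 2017 or Spring 2018) to the regression covariates;
- use a child random intercept or GEE when a child has records in both sessions;
- report the number of distinct children and the number of repeaters, and state which children form the comparison group;
- present an analysis restricted to each child's first BOKS exposure as a sensitivity analysis. As the primary analysis it would remove the already-exposed Fall non-participants, possibly the only comparators, and leave a single-group pre-post comparison.

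**Cost.** One recorded field for Fall 2017 participation at the one school, and wording in Section VI. Enrolment and programme access do not change. Some precision is lost because session overlaps with group: every Spring child in the programme received BOKS and there was no control group, so a session term cannot separate season from programme effect within Spring.

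**A limit to state.** Prior BOKS overlaps with group in the same way. If all comparators are exposed Spring children, the group coefficient in the adjusted model comes down to Fall repeaters against Fall non-participants. Reading it as a first-course effect then assumes that the two courses have equal effects. The added terms make the mixture visible, but they do not supply the missing unexposed control group.
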